Secondary	Bioprosthetic valve failure (BVF); (time-to-first event)	Echo corelab determined	Event driven	Not powered
Secondary	Paravalvular leak severity (categorical)	Echo corelab determined	From baseline to discharge, 1, 12, 24, 36, 48, 60, 72, 84, 96, 108, 120 months	Not powered
Safety	Valve-related mortality (time-to-event)	CRF: clinical events assessed by direct follow-up	Event driven	Not powered
Safety	Myocardial infarction	CRF: clinical events assessed by direct follow-up	Event driven	Not powered
Safety	Coronary obstruction	CRF: clinical events assessed by direct follow-up	Event driven	Not powered
Safety	Major bleeding (VARC-3)	CRF: clinical events assessed by direct follow-up	Event driven	Not powered
Safety	Major vascular complication (VARC-3);	CRF: clinical events assessed by direct follow-up	Event driven	Not powered
Safety	Cardiac structural complication (major)	CRF: clinical events assessed by direct follow-up	Event driven	Not powered
Safety	Need for open heart surgery	CRF: clinical events assessed by direct follow-up	Event driven	Not powered
Safety	Atrial fibrillation/ atrial flutter	CRF: clinical events assessed by direct follow-up	Event driven	Not powered
Safety	Need for permanent pacemaker	CRF: clinical events assessed by direct follow-up	Event driven	Not powered
Safety	Device malpositioning (including embolization and migration)	CRF: clinical events assessed by direct follow-up	Event driven	Not powered
Safety	Acute Kidney Injury stage 3-4	CRF: clinical events assessed by direct follow-up	Event driven	Not powered
Safety	Endocarditis (valve-related)	CRF: clinical events assessed by direct follow-up	Event driven	Not powered
Safety	Clinically significant valve thrombosis (time-to-first event)	CRF: clinical events assessed by direct follow-up	Event driven	Not powered
Exploratory	Prosthesis-patient mismatch severity (categorical)	Echo corelab determined	From baseline to discharge, 1, 12, 24, 36, 48, 60, 72, 84, 96, 108, 120 months	Not powered
Exploratory	Subclinical valve thrombosis (time-to-first event)	CT corelab determined	Event driven	Not powered
Exploratory	Ascending aorta dimension > 50 mm (categorical)	CT corelab determined	From baseline to standard of care interval CTA	Not powered
Exploratory	Change in ascending aorta dimension from baseline to follow up as cm/y (continuous)	CT corelab determined	From baseline to standard of care interval CTA	Not powered

[figure not shown]

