To compare additional safety related outcomes between TAVR and SAVR	Valve-related mortality, Myocardial infarction, Coronary obstruction, Major bleeding (VARC-3), Major vascular complication (VARC-3), Cardiac structural complication (major), Need for open heart surgery, Need for permanent pacemaker, Atrial fibrillation/ atrial flutter, Device malpositioning (including embolization and migration), Acute Kidney Injury stage 3-4, Endocarditis (valve-related), Clinically significant valve thrombosis	These endpoints provide additional comparisons of the frequency of adverse events for the respective procedures
Exploratory		
To compare other imaging outcomes between TAVR and SAVR	Prosthesis-patient mismatch, Ascending aorta dimension > 50 mm, change in ascending aorta dimension	These endpoints provide important metrics on device hemodynamic function, durability and disease progression.

Endpoint Definitions

General principles

Unless otherwise specified, clinical endpoints will be **adjudicated by a Clinical Events Committee (CEC)**. Imaging endpoints will be determined by the **CT Core Laboratory** (Cedars-Sinai Medical Center) and **Echocardiography Core Laboratory** (Cedars-Sinai Medical Center in collaboration with Université Laval in Québec) according to prespecified measurement procedures and charters. Endpoints and timepoints are summarized in Table 1.

Primary Endpoint Components (Hierarchical Composite)

1) All-cause death

Death from any cause occurring after randomization. Date of death will be determined from source documentation and/or vital status ascertainment processes.

2/3) Stroke (disabling and non-disabling)

Stroke is defined as an acute episode of focal or global neurological dysfunction caused by ischemic or hemorrhagic injury to the brain, spinal cord, or retina, with confirmation by at least one of: (a) neurology/neurosurgical specialist assessment; (b) neuroimaging (CT/MRI); or (c) clinical presentation alone when other causes are excluded.

Disabling stroke: mRS ≥ 2 at ~90 days (or last available evaluable visit if 90-day assessment is not available) **and** an increase of ≥ 1 mRS category from pre-stroke baseline.

Non-disabling stroke: mRS < 2 at ~90 days (or last available evaluable visit) **or** no increase of ≥ 1 mRS category from pre-stroke baseline.

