Echocardiography Core Lab (Cedars-Sinai Medical Center in collaboration with Université Laval in Québec)

- **Bioprosthetic valve failure (BVF):** time-to-first BVF event, determined by Echo Core Lab using prespecified criteria in the Core Lab charter and SAP (aligned to contemporary consensus definitions).
- **Paravalvular leak (PVL) severity:** graded by Echo Core Lab per standardized criteria (none/trace, mild, moderate, severe) at prespecified visits.

Safety Endpoints

- Valve-related mortality (time-to-event)
- **Need for open heart surgery;** subsequent need for open heart surgery for any reason (following index procedure).
- **Myocardial infarction :** Using CK-MB preferred if normal baseline: peak CK-MB within 48h $\geq 10 \times$ ULN OR $\geq 5 \times$ ULN plus ≥ 1 supporting criterion (new pathologic Q-waves, new persistent LBBB, flow-limiting angiographic complication, or substantial new loss of viable myocardium on imaging). Alternative troponin thresholds provided if CK-MB not measured.
- **Coronary obstruction:** New partial/complete coronary ostial/epicardial obstruction by prosthesis/native leaflets/embolized material/external compression/instrumentation sequelae, during or after procedure, with objective ischemia or symptoms; classify under cardiac structural complications per severity.
- **Major or life-threatening bleeding (VARC-3);** Bleeding of type 2 or greater (appendix B).
- **Major vascular complication (VARC-3); (time-to-event):** Includes aortic dissection/rupture; vascular injury (arterial/venous) or compartment syndrome resulting in death, BARC/VARC bleeding \geq Type 2, limb/visceral ischemia, or irreversible neurologic impairment; distal embolization causing death/amputation/ischemia/irreversible damage; unplanned endovascular/surgical intervention with those consequences; or closure device failure with those consequences.
- **Cardiac structural complication (major):** Cardiac structure injury/perforation/compromise causing death, VARC bleeding \geq Type 2, hemodynamic compromise/tamponade, or requiring unplanned intervention; major pericardial effusion; coronary obstruction causing death/hemodynamic compromise/MI/unplanned coronary intervention; or coronary access difficulty for needed coronary procedure with major consequences.

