8.10 ADVERSE EVENTS AND SERIOUS ADVERSE EVENTS

8.10.1 Definition of Adverse Events and Reportable Adverse Events for the BELIEVERS trial

An adverse event (AE) is any untoward medical occurrence associated with the use of an intervention, whether or not considered intervention related. Given this study is comparing commercially approved devices, reportable AEs for the BELIEVERS trial will be **restricted to those AEs (both serious and non-serious) corresponding to the study's primary, secondary and safety endpoints derived directly from site reporting** (table 1); those primary, secondary, safety and exploratory endpoints derived from echocardiography or CT corelabs will be reported directly to the DCC by the respective corelabs.

Other reportable AEs complications that can occur include clinical or subclinical valve thrombosis, bioprosthetic valve failure, valve reintervention, valve or heart-failure related hospitalization. Additional details on events that will require reporting will be specified in the MOP and specific guidance in this regard will be provided by the CCC to the sites on site initiation and to the CEC.

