9.4.3 Analysis of The Secondary Endpoint(S)

Key secondary endpoint (hierarchical composite of death and time-averaged KCCQ)

The key secondary endpoint is a hierarchical composite of **(1) all-cause death** and **(2) time-averaged KCCQ overall summary score** within a shared follow-up period by a pair of patients, evaluated using the win ratio framework. Pairwise comparisons will prioritize death; among pairs tied on death status, the KCCQ component will be evaluated using the **time-averaged KCCQ overall summary score** over follow-up. Time-averaged KCCQ will be calculated using all available post-baseline KCCQ assessments and weighted by the time between assessments (i.e., a time-weighted average). The win ratio, 95% confidence interval, and p-value will be reported.

Additional secondary endpoints

Secondary endpoints include patient-reported outcomes, functional outcomes, clinical events, and imaging outcomes as prespecified in Table 1. These will be analyzed using methods appropriate to the endpoint type:

1. **Time-to-event endpoints** (e.g., all-cause death, cardiovascular death, any stroke, disabling stroke, rehospitalization, composite clinical endpoints, aortic dissection, need for surgery of the aorta, BVF/SVD): cumulative incidence functions will be plotted considering non-cardiac death as competing risk for cardiac death; all-cause death as competing risk for any stroke, disabling stroke, rehospitalization, recovery based on QOR-15, aortic dissection, need for surgery of the aorta, BVF/SVD, and need of surgery of aorta as competing risk for aortic dissection. Time-to-event models accounting for competing risk and stratification factors will be used. Results will be summarized as hazard ratios or cumulative incidences with 95% confidence intervals.
2. **Binary endpoints** (e.g., presence of moderate/severe PVL at prespecified timepoints, recovery based on QOR-15, ascending aorta dimension >50 mm, NYHA class): Logistic regression models for repeated measures will be fitted with time, as a categorical covariate, treatment and the interaction between treatment and time as fixed effects. Additionally, models will adjusted by the stratification factors. Results will be summarized as odds ratios between study arms with 95% confidence intervals.

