APPENDIX B.

Term	Definition	Reference / Justification
All-cause mortality	Any death from any cause. Report as time-to-event (Kaplan–Meier) when applicable.	VARC-3 Table 2
Cardiovascular mortality	Death related to heart failure/cardiogenic shock, bioprosthetic valve dysfunction, MI, stroke, thromboembolism, bleeding, tamponade, vascular complication, arrhythmia/conduction disturbance, cardiovascular infection (e.g., mediastinitis/endocarditis), other clear CV cause; includes intraprocedural death, sudden death, and death of unknown cause.	VARC-3 Table 2
Valve-related mortality	Death presumed related to bioprosthetic valve dysfunction (BVD).	VARC-3 Table 2 + Table 12
Non-cardiovascular mortality	Death clearly related to a non-cardiovascular cause (e.g., pneumonia not related to HF, renal/liver failure, non-CV infection, cancer, trauma, suicide).	VARC-3 Table 2
Periprocedural mortality	Death ≤30 days after index procedure OR >30 days but during index hospitalization (includes transfer for continuity of acute care; excludes chronic rehab/nursing home).	VARC-3 Table 2
Early mortality	Death >30 days but ≤1 year after index hospitalization.	VARC-3 Table 2
Late mortality	Death >1 year after index hospitalization.	VARC-3 Table 2
All stroke (overall)	Overt CNS injury (NeuroARC Type 1) including ischemic stroke, hemorrhagic stroke, or stroke not otherwise specified, per Table 3.	VARC-3 Table 3
Ischemic stroke	Acute focal neurologic signs/symptoms in a vascular territory with: symptoms ≥24h (or until death) with neuroimaging/pathology evidence of infarction, or symptoms <24h with imaging/pathology confirmation of infarction in corresponding territory.	VARC-3 Table 3
Haemorrhagic stroke	Acute neurologic signs/symptoms due to intracranial bleeding (intracerebral or subarachnoid) not due to trauma.	VARC-3 Table 3
Stroke, not otherwise specified	Acute neurologic signs/symptoms ≥24h (or until death) without sufficient imaging/pathology to classify as ischemic vs hemorrhagic.	VARC-3 Table 3
Transient ischemic attack (TIA)	Transient focal neurologic signs/symptoms <24h presumed ischemic, without evidence of acute infarction on imaging/pathology (or no imaging performed).	VARC-3 Table 3
Stroke severity (NIHSS)	Mild 0–5; Moderate 6–14; Severe ≥15 (assess at time of stroke diagnosis).	VARC-3 Table 3

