AKI Stage 4 (renal replacement therapy)	New temporary or permanent renal replacement therapy (report separately; exclude chronic dialysis patients from denominator).	VARC-3 Table 10
Myocardial infarction (MI) – periprocedural, Type 5 (\leq 48h)	Using CK-MB preferred if normal baseline: peak CK-MB within 48h \geq 10 \times ULN OR \geq 5 \times ULN plus \geq 1 supporting criterion (new pathologic Q-waves, new persistent LBBB, flow-limiting angiographic complication, or substantial new loss of viable myocardium on imaging). Alternative troponin thresholds provided if CK-MB not measured.	VARC-3 Table 11
Conduction disturbances (reporting framework)	Report baseline and post-procedure conduction status; classify timing (procedural \leq 24h vs delayed >24h), and duration (transient resolved by discharge/ \leq 7d; persistent at discharge/>7d; permanent >30d).	VARC-3 Table 9
New permanent pacemaker	Report type, timing (days from index procedure), and indication (e.g., AV block, sick sinus syndrome). Exclude patients with pre-	VARC-3 Table 9

Term	Definition	Reference / Justification
implantation	existing pacemaker from denominator for “new PPM” rate.	
New-onset atrial fibrillation/flutter	AF/flutter not present at baseline, with ECG characteristics and lasting long enough for a 12-lead ECG or ≥30s rhythm strip. Timing: periprocedural ≤30d vs late/spontaneous >30d.	VARC-3 Table 9
Bioprosthetic valve dysfunction (BVD) – categories	SVD (intrinsic permanent valve changes), NSVD (non-intrinsic abnormalities causing dysfunction, e.g., PVR, malposition, PPM), thrombosis, endocarditis (per criteria below).	VARC-3 Table 12
Endocarditis (valve-related)	Meets ≥1: Duke criteria; abscess/pus/vegetation confirmed at reoperation by histology/microbiology; or abscess/pus/vegetation confirmed on autopsy.	VARC-3 Table 12
Bioprosthetic valve failure (BVF)	Stage 1: clinically expressive BVD (new/worse symptoms or LV remodeling/pulm HTN) or irreversible Stage 3 hemodynamic valve deterioration; Stage 2: aortic valve reoperation/re-intervention; Stage 3: valve-related death.	VARC-3 Table 12
Paravalvular regurgitation (PVR) grading	Grade using integrative echo assessment with either 3-class (none/trace, mild, moderate, severe) or 5-class scheme (none/trace, mild, mild-moderate, moderate, moderate-severe, severe) and Doppler criteria per Table 16.	VARC-3 Table 16

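### Valve-related death is both an event (Appendix B) and a competing event (Section 9.4.3) for bioprosthetic valve failure

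*Protocol*

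**What the plan says.** Four places in the protocol bear on this endpoint.

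- **Appendix B** defines BVF in three stages. Stage 1 is clinically expressed valve dysfunction or irreversible severe haemodynamic deterioration. The other two are clinical events: "Stage 2: aortic valve reoperation/re-intervention; Stage 3: valve-related death". The appendix defines valve-related mortality separately: "Death presumed related to bioprosthetic valve dysfunction (BVD").
- **Section 9.4.3**, under time-to-event endpoints, names "all-cause death as competing risk for any stroke, disabling stroke, rehospitalization, recovery based on QOR-15, aortic dissection, need for surgery of the aorta, BVF/SVD". It makes no exception by cause of death for BVF. Earlier in the same sentence it does split by cause for another endpoint, "considering non-cardiac death as competing risk for cardiac death".
- **Table 1 (Section 1.1)** lists "Bioprosthetic valve failure (BVF); (time-to-first event") as a secondary endpoint that is not powered, and gives the echo core laboratory as its source. Valve-related mortality is a separate safety endpoint in the same table, taken from the case report form.
- **Section 3** puts BVF among the secondary imaging endpoints: "time-to-first BVF event, determined by Echo Core Lab using prespecified criteria in the Core Lab charter and SAP". It adds that the criteria are to follow current consensus definitions. Its general rule is that, unless stated otherwise, "clinical endpoints will be adjudicated by a Clinical Events Committee (CEC"), while imaging endpoints go to the core laboratories.

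On data collection, Section 8.10.1 counts "bioprosthetic valve failure, valve reintervention, valve or heart-failure related hospitalization" among the reportable events. Section 8.10.3.3 requires death, valve reintervention and valve-related mortality to be reported to the coordinating center and the events committee.

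**The concern.** A competing event is one that prevents the event of interest from being observed, so an outcome cannot be both for the same endpoint. Here a valve-related death is one of the things BVF is meant to count, and it is also swept into the competing category because it is a death.

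A time-to-first-event dataset needs one status code per patient. For a patient who reaches Stage 3 without an earlier Stage 1 or Stage 2 event, the protocol supplies two. Coding by Section 9.4.3 removes the gravest form of valve failure from the numerator. Coding by Appendix B departs from the stated analysis. Cumulative incidence and hazard ratio would both depend on a choice the protocol does not make. If valve-related deaths differed between arms, so would the understatement.

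The source label raises a second, softer question. An endpoint assigned to an imaging laboratory includes two stages that are not image readings, and Stage 1 itself can turn on symptoms. No text says how the clinical events enter the determination.

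**Working it through.** The protocol gives no event count, rate or power for BVF, so there is no figure to reproduce. The check is a comparison of the texts, followed by arithmetic for scale only.

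**Step 1. Code the possible patients under each text.**

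| Patient's course | Appendix B | Section 9.4.3, read literally |
|---|---|---|
| Stage 1 finding, later valve-related death | Event at Stage 1 | Event at Stage 1 |
| Reintervention, later death of any cause | Event at Stage 2 | Event at Stage 2 |
| Valve-related death with no earlier Stage 1 or 2 event | Event at Stage 3 | Competing event |
| Death unrelated to the valve, no earlier BVF event | Not an event | Competing event |

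Only the third row conflicts. Reintervention is not named as a competing event for BVF, so nothing in Section 9.4.3 removes Stage 2.

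**Step 2. Is all-cause death a deliberate convention?** The same sentence lets only non-cardiac death compete with cardiac death. The plan therefore does split by cause where death is part of the endpoint. BVF has the same structure but not the same treatment.

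**Step 3. Is the cause category available?** Yes. Valve-related mortality is defined in Appendix B, is a Table 1 safety endpoint and must be reported under Section 8.10.3.3.

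**Step 4. Scale, under an assumption.**

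Inputs: 600 patients per arm (Section 9.4.1). Table 2 (Section 9.2) gives assumed death rates of 5.3% (SAVR) and 7.1% (TAVR), and valve reintervention as the most severe event in 1.7% and 2.3%. These are three-year planning rates. The share *f* of deaths that are valve-related is not in the documents; 2% to 20% is assumed here for illustration.

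- Deaths: 600 × 0.053 = 31.8 (SAVR); 600 × 0.071 = 42.6 (TAVR).
- Reinterventions as most severe event: 600 × 0.017 = 10.2; 600 × 0.023 = 13.8.
- Valve-related deaths = *f* × deaths.
- Share of Stage 2 + 3 events recoded as competing = valve-related deaths ÷ (valve-related deaths + reinterventions).

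| *f* (assumed) | Valve-related deaths, SAVR / TAVR | Share of Stage 2 + 3, SAVR / TAVR |
|---|---|---|
| 2% | 0.64 / 0.85 | 5.9% / 5.8% |
| 5% | 1.59 / 2.13 | 13.5% / 13.4% |
| 10% | 3.18 / 4.26 | 23.8% / 23.6% |
| 20% | 6.36 / 8.52 | 38.4% / 38.2% |

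For a given *f*, these are upper limits at the planning rates. A patient with an earlier Stage 1 or 2 event is already counted, Stage 1 events are left out of the denominator, and Table 2 counts a reintervention only when nothing more severe occurred. Follow-up beyond three years would raise the absolute counts by an amount the documents do not allow one to state.

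**The case against.** The strongest reply is that BVF in this trial is simply an echo endpoint. The note under Table 1 applies Appendix B only where nothing else is specified, and Section 3 does specify something: core laboratory determination by criteria in the charter and the SAP. On that reading Appendix B is a general dictionary, death of any cause is the correct competing event, and there is no conflict. This has some force, because it shows that a coherent endpoint could be built that way. It does not settle the matter. Section 3 also ties the criteria to consensus definitions, and Appendix B defines this very term with Stages 2 and 3. Nor does deferral to the SAP help: the definition and the competing event are both fixed in the protocol, so an SAP faithful to both inherits the conflict.

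A second reply concerns reintervention, and it largely stands. A reader might infer that an echo laboratory cannot record reinterventions, so that the roughly 10 SAVR and 14 TAVR patients implied by Table 2 would be lost from BVF. The documents do not support that. Reintervention is not a competing event, it is reported to the coordinating center and the events committee, and the unseen charter may say how it reaches the determination. Those 10 and 14 patients do not measure the demonstrated error.

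A third reply is that little is lost overall. Reintervention is a tier of the primary composite, with wins and losses reported by level, and valve-related mortality is its own safety endpoint. That is correct and limits the consequence to the BVF result.

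**Conclusion.** The conflict over valve-related death is real and lies within the protocol. Read literally, Section 9.4.3 drops from BVF incidence any patient whose first BVF event is a valve-related death, so BVF is understated by that number. The number is unknown. At three-year planning rates it would be at most about 0.6 to 6.4 patients (SAVR) and 0.9 to 8.5 (TAVR) if 2% to 20% of deaths were valve-related, a range that is assumed and not taken from the documents.

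The source label is a lesser inconsistency: reinterventions may be missed, but this is not shown. A reader might also infer that the comparison is biased against or in favor of a particular arm, or that BVF is the trial's only measure of durability. Neither is supported. The direction depends on valve-related deaths by arm, which are not given, and Section 4.2 links durability to reintervention within the primary composite.

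BVF is a secondary endpoint without stated power, and the primary and key secondary analyses are unaffected. The point is worth correcting before analysis, but it does not threaten the trial's main conclusion.

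**What to change.** Choose one of two consistent definitions and carry it through Table 1, Section 3, Section 9.4.3 and Appendix B.

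1. **Keep the staged definition.** In Section 9.4.3, make only death not related to the valve the competing event for BVF. In Table 1 and Section 3, state that BVF is the first of three events: Stage 1 from core laboratory findings together with the symptom data the definition needs; reintervention adjudicated by the events committee; or valve-related death adjudicated by that committee.
2. **Restrict the endpoint.** Rename it echo-determined valve failure and state that Stages 2 and 3 of Appendix B do not count toward it. All-cause death may then remain the competing event.

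The first option keeps the endpoint that Appendix B describes. Either way the cost is a wording change, with matching text in the SAP and the core laboratory charter. Reinterventions and valve-related deaths are already reportable, so no new data collection is needed.
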